APPENDIX 2 PSORIASIS AREA AND SEVERITY INDEX (PASI)

The PASI is a grading system used for the evaluation of the severity of psoriatic lesions and their response to treatment. The PASI produces a numeric score that can range from 0 to 72. The severity of a subject's disease is calculated as described below:

In the PASI system, the body is divided into 4 regions: the head (h), trunk (t), upper extremities (ux) and lower extremities (lx), which account for 10%, 30%, 20%, and 40% respectively of the total body surface area (BSA). Each of these areas are evaluated for erythema, induration and scaling, which are rated on a scale from 0 to 4.

The scoring system for the signs of disease (erythema, in duration and scaling) is below:

0 = none
1 = slight
2 = moderate
3 = severe
4 = very severe

The scoring system for estimating the area of involvement for psoriatic lesions is outlined below:

0 = no involvement
1 = 1% to 9% involvement
2 = 10% to 29% involvement
3 = 30% to 49% involvement
4 = 50% to 69% involvement
5 = 70% to 89% involvement
6 = 90% to 100% involvement

To aid in the area assessments, the following conventions are followed:

- the neck is considered part of the head
- the axilla and groin are considered part of the trunk
- the buttocks are considered part of the lower extremities

The PASI formula is:

$$\text{PASI} = 0.1(E_h + S_h + I_h)A_h + 0.3(E_t + S_t + I_t)A_t + 0.2(E_{ux} + S_{ux} + I_{ux})A_{ux} + 0.4(E_{lx} + S_{lx} + I_{lx})A_{lx}$$

Clinical assessments of response should be performed by the same assessor(s).

APPENDIX 3 STATIC PHYSICIAN'S GLOBAL ASSESSMENT (SPGA)

The Physician Global Assessment (PGA) is used to determine the subject's psoriasis lesions overall at a given time point. Overall lesions will be graded for induration, erythema, and scaling based on the scales below. The sum of the 3 scales will be divided by 3 to obtain a final PGA score.

Induration (I) (averaged over all lesions; use the National Psoriasis Foundation Reference card for measurement)

- 0 = no evidence of plaque elevation
- 1 = minimal plaque elevation, = 0.25 mm
- 2 = mild plaque elevation, = 0.5 mm
- 3 = moderate plaque elevation, = 0.75 mm
- 4 = marked plaque elevation, = 1 mm
- 5 = severe plaque elevation, = 1.25 mm or more

Erythema (E) (averaged over all lesions)

- 0 = no evidence of erythema, hyperpigmentation may be present
- 1 = faint erythema
- 2 = light red coloration
- 3 = moderate red coloration
- 4 = bright red coloration
- 5 = dusky to deep red coloration

Scaling (S) (averaged over all lesions)

- 0 = no evidence of scaling
- 1 = minimal; occasional fine scale over less than 5% of the lesion
- 2 = mild; fine scale dominates
- 3 = moderate; coarse scale predominates
- 4 = marked; thick, nontenacious scale dominates
- 5 = severe; very thick tenacious scale predominates

Add $I + E + S / 3 =$ (Total Average)

Physician's Static Global Assessment based upon above Total Average

0 = Cleared, except for residual discoloration

1 = Minimal - majority of lesions have individual scores for $I + E + S / 3$ that averages 1

2 = Mild - majority of lesions have individual scores for $I + E + S / 3$ that averages 2

3 = Moderate - majority of lesions have individual scores for $I + E + S / 3$ that averages 3

4 = Marked - majority of lesions have individual scores for $I + E + S / 3$ that averages 4

5 = Severe - majority of lesions have individual scores for $I + E + S / 3$ that averages 5

Note: Scores should be rounded to the nearest whole number. If total ≤ 1.49 , score = 1; if total ≥ 1.50 , score = 2.

[figure not shown]
**APPENDIX 5 AMERICAN COLLEGE OF RHEUMATOLOGY SUBJECT
ASSESSMENT OF PAIN VISUAL ASSESSMENT SCALE**

Measure with a metric ruler. Line on Case Report Form is exactly 10 cm long. Scores should be recorded in millimeter format. DO NOT USE THIS APPENDIX AS SOURCE DOCUMENT OR CASE REPORT FORM.

How much pain have you had because of your condition over the past week? Place a mark on the line below to indicate how severely your pain has been:

No Pain	-----	Pain as Bad as it Could be
---------	-------	----------------------------------

APPENDIX 6 SUSTAINED ELEVATED LIVER SAFETY ABNORMALITIES FLOW CHART

^a In subjects with repeat ALT or AST > 3X ULN but ≤ 10X ULN, only subjects with TB ≤ 2.0X ULN at Step 1 should be followed according to Step 2b. Subjects with an initial TB and confirmatory repeat TB > 2.0X ULN should be followed according to Step 2d.

^b additional assessments to be performed (AE assessment, PE, review of current medical history including focused review of risk factors for liver diseases and collection of blood samples [specialized liver panel or liver discontinuation panel](see below)).

^c Confirmatory repeat AST, ALT, ALK-P and TB should be obtained every 3 days following receipt of prior laboratory results, until the ALT and AST are ≤ 2X ULN or until ALT and AST are at or below baseline levels. The frequency of retesting can decrease to once a week or less if abnormalities stabilize and the subject is asymptomatic.

Specialized Liver Panel:

For subjects who are being monitored frequently as a result of confirmed AST and/or ALT > 3X ULN, additional central laboratory tests will be performed within 3 days of receipt of confirmatory results. These laboratory tests will study the possible causes of the increased ALT and/or AST and/or TB, and may include, but are not limited to, the following tests:

- Hepatitis A IgM
- Hepatitis BsAg
- Hepatitis B Core Ab IgM
- Hepatitis C virus RNA or RIBA
- Hepatitis C Ab
- Hepatitis E IgM
- Epstein-Barr Virus (EBV) IgM Ab
- Lactate Dehydrogenase (LDH)
- Gamma-glutamyl-transpeptidase (GGT)
- Carbohydrate deficient transferrin (CDT)
- Prothrombin time (PT/INR)
- Iron Panel - iron, ferritin, total iron binding capacity (TIBC)
- Immunology Panel including Antinuclear Antibody (ANA), Anti-Smooth Muscle Antibody (SMA) and Anti-Liver/Kidney Microsomal Antibody (Anti-LKM)
- Anti-tissue Transglutaminase Antibody

Liver Discontinuation Panel:

For subjects who are discontinued from the study as a result of sustained elevated liver safety abnormalities, additional central laboratory tests will be performed at the time of Early Termination (End-of-Treatment) visit. Similar to the Specialized Liver Panel, these laboratory tests will study the possible causes of the increased ALT and/or AST and/or TB, and may include, but are not limited to, the following tests:

- Cytomegalovirus (CMV) IgM Ab
- Herpes Simplex Virus (HSV) 1 and 2
- Ceruloplasmin
- Toxoplasmosis
- Alpha-1 antitrypsin

2 STUDY DESCRIPTION

[figure not shown]
2.1 Study Design

This is a 12 week, multi-center, randomized double-blind, placebo-controlled, parallel-group multiple oral dose study in subjects with moderate to severe psoriasis. Subjects will be randomly assigned to one of six treatment groups, i.e., to receive BMS-986165 (3mg every other day (Q2D); 3mg every day (QD); 3mg twice daily (BID); 6mg BID; 12mg QD) or placebo. Subjects will undergo screening evaluations to determine eligibility within 28 days prior to administration of study medication.

This is an outpatient study. Subjects will receive BMS-986165 or placebo capsules to be taken at home.

The study design schematic is presented in Figure 1.

Figure 1: Study Design Schematic

Q2D=every other day, QD=every day, BID=twice daily

The approximate duration of the study is 20 weeks (143 days). This includes a 4-week screening period (28 days), a 12-week treatment period (85 days), and a 4-week follow-up period (30 days).

The start of the trial is defined as the date of the first Screening Visit (date of signing the informed consent) for the first subject screened. The end of trial is defined as the last visit or scheduled procedure shown in the Time & Events schedule (Table 5.1-1 and Table 5.1-2 of the study protocol) for the last subject. Study completion is defined as the final date on which data for the primary endpoint was or is expected to be collected, if this is not the same.

2.2 Treatment Assignment

After completion of all screening evaluations, on Day 1, all eligible subjects will be randomly assigned to 1 of 6 treatment arms (BMS-986165, 3mg Q2D; BMS-986165, 3mg QD; BMS-986165, 3 mg BID; BMS-986165, 6mg BID; BMS-986165, 12mg QD; and Placebo) in an equal ratio.

Enrolled subjects meeting inclusion and exclusion criteria will be eligible to be randomized. Randomization numbers will be assigned prior to dosing. During the screening visit, the investigative site will call into the enrollment option of the Interactive Web Response System (IWRS) designated by BMS for assignment of a 5-digit subject number that will be unique across all sites. Enrolled subjects, including those not dosed, will be assigned sequential subject numbers starting with 00001, (e.g., 00001, 00002, 00003....00010). The patient identification number (PID)

will ultimately be comprised of the site number and subject number. Once it is determined that the subject meets the eligibility criteria following the screening visit, the investigative site will call the IWRS to randomize the subject. Randomization will be stratified by the use of previous treatment with a biologic (yes/no) and region (Japan vs rest of world).

Specific instructions (including an enrollment/randomization worksheet) for the central enrollment and randomization procedure using an IWRS will be provided to the site.

2.3 Blinding and Unblinding

This is a double-blinded study. The subjects and all site personnel, including the investigator, the site monitor, and the study team, will be blinded. The study will be kept in the blinded nature until the last patient last visit, after which the database undergoes a final lock and unblinding for the final analysis.

Blinding of treatment assignment is critical to the integrity of this clinical study. However, in the event of a medical emergency or pregnancy in an individual subject in which knowledge of the investigational product is critical to the subject's management, the blind for that subject may be broken by the investigator. The subject's safety takes priority over any other considerations in determining if a treatment assignment should be unblinded.

Before breaking the blind of an individual subject's treatment, the investigator should determine that the unblinded information is necessary, (i.e., that it will alter the subject's immediate management). In many cases, particularly when the emergency is clearly not related to the investigational product, the problem may be properly managed by assuming that the subject is receiving active product. It is highly desirable that the decision to unblind treatment assignment be discussed with the medical monitor, but the investigator always has ultimate authority for the decision to unblind. The principal investigator should only call in for emergency unblinding AFTER the decision to discontinue the subject has been made.

In cases of accidental unblinding, contact the medical monitor and ensure every attempt is made to preserve the blind.

Any request to unblind a subject for non-emergency purposes should be discussed with the medical monitor.

In case of an emergency, the investigator(s) has unrestricted access to randomization information via the IWRS and is capable of breaking the blind through the IWRS system without prior approval from sponsor. Following the unblinding the Investigator shall notify the medical monitor and/or study director.

For analyses for the Independent Data Monitoring Committee (IDMC), a separate unblinded study team, comprising an unblinded biostatistician(s) and unblinded programmer(s), will be performing the required analyses.

2.4 Protocol Amendments

Not applicable.

2.5 Data Monitoring and Other External Committees

An Independent Data Monitoring Committee (IDMC) will be established to monitor data on an ongoing basis to ensure the continuing safety of subjects enrolled in this study, to ensure the integrity of the blinded nature of the study. An IDMC charter will be developed which will specify the roles and responsibilities of the members and interim decision rules. The Sponsor Steering Committee will receive and act on the recommendations from the IDMC. A firewall will be established to ensure the maintenance of the study blind for the Sponsor, the investigational site staff, and study subjects and their study partners.

Data summaries and listings will be provided to the IDMC to facilitate their safety assessment at the regularly scheduled times and on an ad hoc basis if needed. The safety review includes serious adverse events and events of special interest, focusing on early signal detection. Further details on the frequency, content and methods of data reports to the IDMC are outlined in the IDMC charter and IDMC Statistical Analysis Plan (SAP).

3 OBJECTIVES

3.1 Primary

- To compare the proportion of subjects with moderate to severe psoriasis experiencing a 75% improvement as measured by a reduction in PASI score (PASI-75) after 12 weeks of treatment between doses of BMS-986165 and placebo
- To assess the safety and tolerability of multiple oral doses of BMS-986165 in subjects with moderate to severe psoriasis

3.2 Secondary

- To assess that the proportion of subjects experiencing a 75% reduction in PASI score in the most efficacious treatment group
- To compare the proportions of subjects experiencing a 75% reduction in PASI score between treatment groups
- To assess a positive trend between treatment groups of BMS-986165 and proportion of subjects experiencing a 75% reduction in PASI score after 12 weeks of treatment
- To assess clinical efficacy of BMS-986165 as measured by improvement in skin disease area and severity indices PASI-50, -75, -90 and -100 over time in subjects with moderate to severe psoriasis
- To assess a significantly higher proportion of subjects achieving Static Physician's Global Assessment (sPGA) score of "0" ("cleared") or "1" ("minimal") after 12 weeks of treatment with BMS-986165 than after 12 weeks of treatment with placebo
- To assess improvement by BMS-986165 in Dermatology Life Quality Index (DLQI)
- To assess the trough concentrations of BMS-986165 in subjects with moderate to severe psoriasis

[REDACTED]

4 ENDPOINTS

4.1 Primary Efficacy Endpoint

The primary endpoint is the response rate in PASI-75: the proportion of subjects with moderate to severe psoriasis experiencing a 75% improvement (reduction from baseline) in PASI score at Day 85.

4.2 Secondary Endpoints

The following secondary endpoints will be evaluated in this trial:

- Proportion of subjects at Day 85 with PASI-50, PASI-75, PASI-90, PASI-100
- Change from baseline in DLQI scores at Day 85
- Change from baseline in body surface area (BSA) at Day 85
- Proportion of subjects at Day 85 with sPGA score of 0 or 1
- Pharmacokinetics (PK) parameter: Ctrough

4.3 Primary Safety Endpoint

- The safety and tolerability of BMS-986195 will be assessed by the incidence, potential significance, and clinical importance of adverse events measured during multiple doses of BMS- 986195 and up to 30 days after the last dose, as determined by medical review of adverse event reports, vital sign measurements, electrocardiograms (ECGs), and results of physical examination and laboratory tests.

[REDACTED]

5 SAMPLE SIZE AND POWER

The sample size calculation is driven by several considerations.

The first consideration is to compare the response rate in PASI-75, the proportion of subjects with moderate to severe psoriasis experiencing a 75% improvement in PASI score after 12 weeks, between BMS-986165 and placebo arms. With a one-sided, two-sample Fisher's exact test at significant level 0.05, a sample size of 42 per arm will provide at least 99% power to detect 50% increase in the PASI-75 response rate in an active arm (i.e., 60% response rate) compared to the placebo assuming the response rate is 10% in the placebo arm.

The second consideration is to assess the response rate in PASI-75 in active dose arms. Data from 42 treated subjects per arm will produce a two-sided 95% confidence interval (CI) with a margin of error at most 15.1% (half width) using normal approximation.

The third consideration is to compare the response rates in PASI-75 in two active arms. With a one-sided, two-sample Fisher's exact test at significant level 0.05, 42 subjects per arm will provide at least 82% power to detect at least 30% difference in the response rate in PASI-75 between any two active dose arms.

The proposed sample size is mainly driven by the third consideration. In addition, administration of BMS-986165 to 42 subjects in each active treatment group provides 34%, 88%, and 99% probability of observing at least one occurrence of any adverse event that would occur with 1%, 5%, or 10% incidence rate respectively.

6 STUDY PERIODS, TREATMENT REGIMENS AND POPULATIONS FOR ANALYSES

6.1 Study Periods

The following periods are defined in this SAP for the purpose of analyses and reporting.

Screening period: Covers the time period which starts from the day of enrollment and lasts until the initiation of randomized double-blind treatment.

Treatment period: Starts at the time of the first dose of blinded treatment (BMS-986165 or placebo) and lasts until the date of the last dose of double-blinded treatment.

Follow-up period: Starts at the date of the last dose of blinded treatment and lasts 30 days post.

6.2 Treatment Regimens

Subjects will receive one of the following treatments for 12 weeks:

- BMS-986165 3mg Every Other Day (Q2D)
- BMS-986165 3mg Every Day (QD)
- BMS-986165 3mg Twice Daily (BID)
- BMS-986165 6mg BID
- BMS-986165 12mg QD
- Placebo

6.3 Populations for Analyses

The following subject populations will be considered in this trial:

- All Enrolled Subjects: All subjects who sign an informed consent.
- All Randomized Subjects: All subjects who are randomized to a treatment.
- All Randomized and Treated Subjects: All randomized subjects who receive at least one dose of the study medication. Subjects will be grouped according to the treatment to which they are randomized by IWRS at the start of the study.
- As-Treated Analysis Population: All subjects who have received at least one dose of study medication. Subjects will be grouped according to the treatment that they actually receive as opposed to the treatment to which they are randomized. Subjects will be grouped on an as-randomized basis unless the subject received the incorrect medication for the entire treatment period. In that case, the subject will be analyzed in the treatment group associated with the incorrect medication he/she receives.
- Efficacy Analysis Population: All Randomized and Treated Subjects.
- Biomarker Analysis Population: All subjects that receive any study medication and have at least 1 post-treatment biomarker measurement.
- Pharmacokinetic Population: All subjects who receive any study medication and have any available concentration-time data.
- Per-Protocol Population: All randomized subjects without relevant protocol deviations (Section 7.2.1). The primary efficacy analysis will be performed using this population if there are more than 10% of the study subjects with relevant protocol deviations.

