7.2 Study Conduct

7.2.1 Relevant Protocol Deviations

Relevant protocol deviations, which could have an impact on the primary efficacy endpoint, will be identified for all subjects who are randomized and receive study medication during the treatment period. Details of relevant protocol deviations are provided in Appendix 1.

All subjects with relevant protocol deviations will be identified prior to database lock and unblinding of treatment assignment. All relevant protocol deviations will be listed and summarized by treatment group based on All Randomized and Treated Subjects.

If there are more than 10% of the study subjects with relevant protocol deviations, a Per-Protocol analysis excluding these subjects will be performed for the primary efficacy endpoint.

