7.5 Efficacy

Unless otherwise specified, the efficacy data will be presented using the Efficacy Analysis population.

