7.5.6 Per-Protocol Analyses

If at least 10% of total subjects in efficacy analysis population demonstrate relevant protocol deviations, a per-protocol analysis may be performed. A Per-protocol (PP) analysis population will exclude all subjects with at least one relevant protocol deviation (defined in Appendix 1) from the efficacy analysis population. A per-protocol analysis will be carried out for the primary efficacy

endpoint based on the PP analysis population. The grouping scheme will be the same as in the primary efficacy analysis.

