APPENDIX 1 RELEVANT PROTOCOL DEVIATIONS

Eligibility Deviations:

- Subjects with a diagnosis of plaque psoriasis for < 6 months
- Body mass index (BMI) not within 18-40 kg/m² or total body weight ≤ 50 kg (110 lb.)
- Subject with psoriatic plaques cover < 10% of body surface area (BSA)
- Subject with PASI score < 12 or sPGA < 3

- Diagnosis of non-plaque psoriasis

Incorrect dosing:

- Subjects who receive treatment different than randomized group
- Subjects taking less than 80% or more than 120% of the planned medication during the entire treatment period
- Randomized subjects who do not take any blinded study medication for \geq two consecutive weeks
- Restricted and Prohibited medications (refer to Protocol Section 3.4.1):
- Subjects receiving prohibited concomitant treatments while on study therapy. The prohibited and/or restricted treatments are described in Table 3.4.1-1 of the study protocol.

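### SAP 6.3, read literally, moves the primary efficacy analysis to the per-protocol set once more than 10% of subjects deviate; the SAP never says which population then governs

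*SAP*

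**What the plan says.** SAP 6.3 defines the Efficacy Analysis Population as all subjects randomised and treated. It defines the Per-Protocol Population as all randomised subjects without relevant deviations, refers to Section 7.2.1, and adds: "The primary efficacy analysis will be performed using this population if there are more than 10% of the study subjects with relevant protocol deviations".

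SAP 7.2.1 states that above 10% "a Per-Protocol analysis excluding these subjects will be performed for the primary efficacy endpoint". It adds that relevant deviations "will be identified for all subjects who are randomized and receive study medication during the treatment period", and on timing: "All subjects with relevant protocol deviations will be identified prior to database lock and unblinding of treatment assignment".

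SAP 7.5 sets the default: "Unless otherwise specified, the efficacy data will be presented using the Efficacy Analysis population".

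SAP 7.5.6 reads: "If at least 10% of total subjects in efficacy analysis population demonstrate relevant protocol deviations, a per-protocol analysis may be performed". Its per-protocol set "will exclude all subjects with at least one relevant protocol deviation (defined in Appendix 1) from the efficacy analysis population". It also mentions the primary efficacy analysis as a separate item whose grouping the per-protocol analysis will follow.

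SAP Appendix 1 lists the deviations. Some are eligibility failures, fixed at baseline. Others arise after randomisation: wrong treatment, intake outside a range ("Subjects taking less than 80% or more than 120% of the planned medication during the entire treatment period"), a gap of two or more consecutive weeks without study medication, and prohibited treatments.

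Protocol 8.2 has no per-protocol set. It assigns efficacy analyses to all randomised subjects and later bases efficacy summaries on all treated subjects.

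**The concern.** The subject of the 6.3 sentence is the primary efficacy analysis itself, and no word such as *also* or *supportive* limits it. A programmer who follows it literally would run the primary comparison on the per-protocol set whenever the trigger is met. The default in 7.5 gives way to anything specified elsewhere, so it does not settle the matter.

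At stake is the protection that randomisation gives the primary comparison. Intake, treatment gaps and prohibited medication can depend on the assigned arm and on how the subject is doing. Removing subjects for these reasons can make the arms differ in ways that have nothing to do with the drug. Identifying deviators before unblinding stops anyone from choosing the population on known results. It does not remove the bias from the exclusions themselves.

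**Working it through.** **1. The passages side by side**

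| | SAP 6.3 | SAP 7.2.1 | SAP 7.5.6 |
|---|---|---|---|
| Trigger | more than 10% | more than 10% | at least 10% |
| Denominator | study subjects | study subjects | efficacy analysis population |
| Verb | will | will | may |
| What is run | the primary efficacy analysis | a per-protocol analysis of the primary endpoint | a per-protocol analysis, distinct from the primary one |
| Base set | all randomised | deviations sought in dosed subjects | Efficacy Analysis Population |

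Sections 7.2.1 and 7.5.6 fit an additional analysis. Section 6.3 fits either a repeat or a replacement. No section ranks the two populations.

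**2. When the trigger is met**

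Inputs: six arms in equal ratio (SAP 2.2) and 42 per arm (SAP 5). The total is derived: 6 × 42 = 252.

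- 0.10 × 252 = 25.2, so *more than* and *at least* 10% are both first met at 26 subjects.
- The triggers separate only when 10% of the relevant denominator is a whole number. With 250 treated of 252 randomised (assumed), 7.5.6 is met at 25 and 6.3 at 26, a gap of one subject.

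**3. The plan's own power figure, and the effect of losing deviators**

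Method: exact enumeration of the one-sided Fisher test at 0.05 over two binomials, 60% against 10%.

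- 42 against 42: 0.9997. This reproduces the plan's statement of at least 99%.
- 37 against 38: 0.9989.

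**4. Illustrative bounds on the estimated difference**

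Assumptions: 26 deviators spread as evenly as possible (4 × 4 + 2 × 5 = 26), so five are excluded from one active arm and four from placebo. Responders are set near the planning rates: 25/42 = 59.5% and 4/42 = 9.5%.

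- Full set: (25 − 4)/42 = 50.0 points.
- Lowest: all five excluded active subjects are responders and no excluded placebo subject is. 20/37 − 4/38 = 54.1% − 10.5% = 43.5 points (from unrounded rates).
- Highest: no excluded active subject is a responder and all four excluded placebo subjects are. 25/37 − 0/38 = 67.6 points.
- All excluded subjects are non-responders: 25/37 − 4/38 = 57.0 points. With four active subjects excluded instead: 25/38 − 4/38 = 55.3 points.

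The two ends are arithmetic limits, not forecasts.

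**5. Are early stoppers excluded?**

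The intake criterion in Appendix 1 refers to the treatment period, which SAP 6.1 ends at the date of the last dose. On that definition, doses missed after stopping do not count towards the 80–120% range. SAP 7.4.2 points the same way, because its compliance summary leaves out doses missed through premature discontinuation. The two-week criterion names no period and stays open. If early stoppers were excluded, their outcomes could go either way. Those who leave the trial are non-responders under SAP 8.3.1. Those who only stop the drug are to be followed under protocol 3.6.1 and may have an observed Day 85 response.

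**The case against.** The strongest reply is that replacement is the less natural reading. The 6.3 entry points to 7.2.1, which describes a per-protocol analysis of the primary endpoint. Section 7.5.6 has its own heading and contrasts this analysis with the primary one, and 7.5 names a default population. Deviators are fixed before unblinding, so nobody could switch on seen results. Most of this stands: supportive use is the likely intent, and data-driven choice is limited. But likely intent is not a stated rule, and the only sentence about the primary efficacy analysis under this trigger sends it to the per-protocol set.

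A reader might infer four stronger points that the documents do not support:

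- *Early stoppers would certainly be removed from the primary comparison.* SAP 6.1 suggests otherwise for the intake criterion; only the two-week criterion leaves the question open.
- *A randomised, never-dosed subject would remain in the 6.3 set.* Section 7.2.1 seeks deviations only in dosed subjects, but the two-week criterion in Appendix 1 is worded for randomised subjects, and a never-dosed subject would appear to meet it.
- *Protocol 8.2 rules out replacement in particular.* It has no per-protocol set at all, so it is equally silent on a supportive one. It also names two different efficacy sets.
- *The differing thresholds matter in practice.* At 252 they coincide.

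**Conclusion.** SAP 6.3 is wrong as written. Its literal wording moves the primary comparison to a set selected partly on post-randomisation events, and nothing in the SAP says which population governs once the trigger is met. It would go too far to say that the plan definitely replaces its primary population: the wording permits this, while 7.2.1 and 7.5.6 lean against it.

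The size and direction of any bias cannot be fixed, because no deviation rate is given. The range of 43.5 to 67.6 points around 50.0 rests on assumed counts at the minimum trigger and on extreme response patterns. The effect is on the estimated response rates. Power against placebo is essentially unaffected, though that figure holds for the planning rates of 60% and 10%. If the per-protocol analysis is only additional, the primary result stands unchanged.

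**What to change.** Replace the sentence in SAP 6.3 with: *The primary analysis always uses the Efficacy Analysis Population with the Section 8.3.1 imputation; if the deviation threshold is met, a per-protocol analysis is performed as supportive only.*

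Use one threshold, one denominator, one base set and one verb in 6.3, 7.2.1 and 7.5.6.

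Optionally, state in Appendix 1 that the treatment-period definition in SAP 6.1 applies to the 80–120% criterion, and say whether the two-week criterion covers time after discontinuation.

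The cost is SAP wording only, before database lock. The sample size and the planned power do not change.
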